Health Planning Society, Westside Health Network, Seniors Outreach Bureau) serve large and different populations of seniors (>300 seniors) so overlap in membership is not expected to be an issue.

**Sampling and Recruitment:** The study sample will include older adults  $\geq 65$  years of age (men and women) who attend a local Senior's Centre or organization, report having some UI symptoms, are independent living, ambulatory, with no more than mild cognitive impairment, able to read and write in English or have someone who can assist with reading the data collection information and can complete a paper survey independently. Older adults will be excluded if they have cognitive impairment, require more than minimal assistance with completing the survey, or have any impairment (e.g., vision) that would make self-screening and follow up challenging. They must also never have been referred to a UI specialist or program in the past.

Following ethics approval, eligible older adults will be recruited through a letter of invitation sent through e-mail distribution lists of our participating seniors centres/organizations (**see Letter of Invitation**). Based on other UI studies, in which there was a 14% self-referral rate without an intervention, we hypothesize a 61% incremental increase in self-referral in the arm receiving the intervention. The sample size required to detect an improvement in self-referral (with 80% power,  $p < .05$ ) to a health professional (e.g., UI specialist) is 24 participants (12 older adults per arm). Drop-out or attrition is common in research studies. In factoring the potential for a drop-out rate of 50%, a sample size of 36 participants will be recruited. Excel randomization function will be used to assign participants to one of the two arms (the arm receiving the self-screening process or the arm not receiving this process). The randomization assignments (allocations) will be placed in individual sealed envelopes. After informed consent is obtained, the Research Assistant (RA) will choose the next available envelope to reveal which arm the study participant will be assigned.

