### **Data Collection:**

*Pre-test:* Prior to implementation, the self-screening tool will be pre-tested with 5 older adults attending participating seniors centres/organizations. The purpose of the pretest will be to identify any implementation issues such as recruitment, administration, understanding and ease of use of the self-screening tools.

*Procedures:* Older adults assigned to both groups will receive follow up from the RA who will provide details about the study and answer any questions. Prior to randomization, consenting older adults from both groups will complete a demographic (e.g., age, sex, highest level of education, household income), health history profile (e.g., co-morbidities, history of previous referrals for UI, medications) (**see Demographic and Health History Profile**) and a quality of life questionnaire (**see The King's Health Questionnaire**).

Three months following study entry participants from both groups will receive a phone follow-up to obtain information about actions they have taken re IU (e.g., self/physician

referral), UI symptoms,  treatments received, satisfaction with care (**See Three Month Follow up Questionnaire**), and changes in quality of life. The follow up phone call will be recorded. It is expected the baseline and 3 month follow up data collection will take approximately 20-30 minutes to complete.

The primary outcome will be the numbers of older adults who take action to receive help for their UI during the 3-month follow-up from study entry: self-referral to the local UI clinic, appointment with GP about their UI, and/or referral to a specialist (urologist or urogynecologist or gynecologist), or other action. Secondary outcomes will include: treatments received, satisfaction with care, changes in quality of life.

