#### *Primary analysis:*

The study hypothesis is that older adults exposed to the self-screening process will follow-up with health professionals to receive help for their UI condition more often than the control group. To test this hypothesis, investigators will calculate the proportion (with 95% CI) of participants who self-report as having self-referred to a health professional (binary yes/no response) during the study period for each group. A chi-square test will be conducted to determine if the self-screening process is associated with self-referral to a health professional. In addition, a logistic regression analysis will be conducted to model the odds of self-referring among people who have undergone self-screening, adjusting for demographics, and health history variables. Bivariate analysis will be conducted and variables significantly associated with self-referral will be entered into the model. Since the study sample size will only allow for having 3 variables in the

model, more than one regression model may be necessary. If this is the case, a Bonferroni adjustment will be used to account for multiple comparisons.

*Secondary analysis:*

Quality of life scores will be compared within and between groups. For the within group comparison a two-sided dependent t-test will be conducted using the pre-study and 3-month quality of life scores for each group. To determine if a change in quality of life (difference between pre-study and 3-month quality of life scores) is statistically significant and mixed between-within subjects analysis of variance will be conducted.

All participants will complete a Urinary Symptoms questionnaire (ICIQ-FLUTS) which consists of ordinal categorical responses to questions related to urinary symptoms. Each question has five response options. For each question, each response category will be assigned a numeric value depending on the severity of the symptom (1= no symptoms; 5=severe symptoms). For each participant, improvement in symptoms will be determined by a reduction in the ordinal value. Improvement in UI symptoms will be compared between groups using a chi-square test.

Investigators are also interested in knowing if self-screening results in a higher proportion of participants initiating medication of UI during the study period. Therefore, the proportion of participants in each group who started medication for UI during the study period will be compared using a chi-square test.

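### The medication-initiation comparison counts people already on UI medication at entry as non-starters; an at-risk denominator should be added

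*Combined protocol and SAP*

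**What the plan says.** The medication endpoint is in the combined protocol and SAP under Data Analysis, Secondary analysis. The stated interest is whether self-screening leads more participants to initiate UI medication. The analysis is that "the proportion of participants in each group who started medication for UI during the study period will be compared using a chi-square test".

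Under Methods, Sampling and Recruitment, participants must "report having some UI symptoms". The only criterion on previous UI care is this: "They must also never have been referred to a UI specialist or program in the past". Current UI medication is not mentioned.

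Under Methods, Control Group, the protocol describes usual GP care as minimal, but says that drug treatment is offered in some cases.

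Under Data Collection, Procedures, both groups complete before randomisation a "health history profile (e.g., co-morbidities, history of previous referrals for UI, medications"). The Data Analysis section uses these items to describe the sample, overall and by group, and as candidate covariates in the primary model. It does not use them to define who can initiate medication.

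**The concern.** Initiation is an event that only a person not yet on treatment can have in the plain sense. The entry criteria let in someone whose GP has already prescribed a UI drug without any specialist referral. If that person continues on the same drug, the analysis records a non-starter, although self-screening had no opportunity to bring about a start.

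Each such person lowers the observed start proportion in their arm. The reported proportions then mix two things: how often untreated people start, and how many people arrived already treated. With so few participants, a handful of baseline users moves a percentage visibly. That matters in a pilot, whose proportions may be carried into the planning of a larger trial.

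**Working it through.** **The plan's own figure.** The only sample size in the document is for self-referral: "in which there was a 14% self-referral rate without an intervention, we hypothesize a 61% incremental increase in self-referral", for which the stated requirement "is 24 participants (12 older adults per arm"). Reading 61% as percentage points gives 14% vs 75%. With two-sided alpha 0.05 (sidedness is not stated) and 80% power, and mean rate 0.445:

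n = [1.96 x sqrt(2 x 0.445 x 0.555) + 0.842 x sqrt(0.14 x 0.86 + 0.75 x 0.25)]^2 / 0.61^2 = 9.1, so 10 per arm; with continuity correction 12.2, so 13 per arm.

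Fisher exact power at 12 per arm is 83%. The stated 12 per arm is therefore reasonable for the primary outcome, but the plan gives no power for medication initiation. I use 12 per arm below as the base case.

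**Assumptions.** The document gives neither m, the share already on UI medication, nor start rates. I take m from 0 to 0.5 and start rates among non-users of 10% (control) and 40% (intervention). Baseline users are assumed to stay on the same drug.

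**Dilution.** In each arm, observed proportion = start rate x (1-m). So:
- difference = (0.40 - 0.10) x (1-m)
- ratio = 0.40(1-m) / 0.10(1-m) = 4.0 for every m

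**Power.** The normal approximation is Phi{[d x sqrt(n) - 1.96 x sqrt(2 x pbar x (1-pbar))] / sqrt(p1(1-p1) + p2(1-p2))}. For all participants it uses n = 12 and rates multiplied by (1-m). For the at-risk analysis it uses n = 12(1-m) and the undiluted rates. The exact figures enumerate all outcomes of the uncorrected chi-square test; the at-risk column averages over the binomial number of non-users in each arm.

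| m | Difference, all participants | Approx. power, all | Approx. power, at-risk | Exact power, all | Exact power, at-risk |
|---|---|---|---|---|---|
| 0 | 30 points | 39.0% | 39.0% | 38.7% | 38.7% |
| 0.1 | 27 | 34.5% | 35.5% | 33.2% | 37.5% |
| 0.2 | 24 | 30.4% | 31.9% | 27.8% | 33.5% |
| 0.3 | 21 | 26.4% | 28.2% | 22.4% | 28.6% |
| 0.5 | 15 | 19.2% | 20.9% | 11.8% | 18.6% |

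At 18 per arm the approximate figures are 49.1% vs 50.5% at m = 0.1 and 37.7% vs 40.7% at m = 0.3.

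**Type I error.** With a 30% start rate among non-users in both arms and 12 per arm, the all-participant chi-square rejects 4.9%, 4.6%, 4.3% and 4.0% of the time at m = 0, 0.1, 0.2 and 0.3. The at-risk version rejects 5.3% to 5.4% at m = 0.1 to 0.3, so part of its exact gain in power comes from being less conservative.

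**Chance imbalance.** Suppose non-users in both arms start at 30%, with 4 of 12 baseline users in one arm and 1 of 12 in the other. Expected proportions are 0.30 x 8/12 = 20.0% and 0.30 x 11/12 = 27.5%, a gap of 7.5 points. In people, that is 2.4 vs 3.3 expected starters. By binomial calculation, the arms differ by three or more baseline users with probability 8%, 20% and 26% at m = 0.1, 0.2 and 0.3.

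**The case against.** A proportion of everyone enrolled is a legitimate quantity: it describes the effect of offering self-screening to this population as it comes. Randomisation balances m in expectation, so the ratio is preserved and the test stays valid. This stands. A reader might infer from the imbalance example that the planned analysis is biased or produces false positives. It does not. The 7.5-point gap is ordinary sampling variation, it amounts to less than one expected starter, and the test already allows for it. The baseline table by group would also show an imbalance in recorded medications.

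It can also be said that baseline users are not strictly unable to start, since they may add or switch a UI drug. The plan does not say whether that counts. This stands too, and it is a reason to define the term rather than to leave the denominator open.

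The share m may be small, because the protocol describes usual care as very often absent. That limits the size of the problem but does not remove it.

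Finally, medications appear only as an example item in the baseline profile, and the form is not in the document. Whether it identifies UI drugs cannot be confirmed.

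What remains is that an endpoint about initiation should be reported among people who have yet to initiate, and the plan does not do so.

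**Conclusion.** The concern holds for the medication endpoint as a matter of dilution and interpretability. The absolute difference is multiplied by (1-m), a loss of 10% at m = 0.1 and 30% at m = 0.3. Under the assumed 10% and 40% start rates the loss of power that a changed denominator can recover is modest. The result rests on an assumed m, assumed start rates, and baseline users not counting as starters. It does not bear on the primary outcome.

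A reader might extend the point to symptom improvement, since a question already at the lowest level cannot fall. The document does not support that extension. It says that "improvement in symptoms will be determined by a reduction in the ordinal value" for each participant, but states no denominator and does not say how questions combine. Everyone enters with some UI symptoms. The baseline instruments listed for both arms do not include the ICIQ, so a control-arm baseline for symptoms may not exist.

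**What to change.** In Data Analysis, Secondary analysis:
- Calculate the initiation proportion, and its chi-square comparison, among participants not taking UI medication at baseline, using the medications recorded before randomisation.
- State that adding or switching a UI drug in a baseline user is reported separately and does not count as starting.
- Report the number excluded from the denominator in each arm.
- Keep the all-participant proportion as a supplementary line.

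Check that the Demographic and Health History Profile identifies drugs taken for UI; if it does not, add that item.

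Baseline status precedes randomisation, so the restriction keeps the randomised comparison. The cost is SAP wording, possibly one item on a form already in use, and a slightly smaller denominator: with 12 per arm, about 11 at m = 0.1 (12 x 0.9 = 10.8) and about 8 at m = 0.3 (12 x 0.7 = 8.4).
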